6.2 IMPORTANT PROTOCOL DEVIATIONS

Data discrepancies and deviations from the CTP will be identified for all treated subjects.

Section 7.3 of the CTP: *Important protocol deviation (IPD) categories will be specified in the TSAP, IPDs will be identified no later than in the Report Planning Meeting, and the IPD categories will be updated as needed.*

Consistency check listings (for identification of deviations from time windows) and a list of protocol deviations (e.g. deviations in drug administration, in blood sampling times, etc.) will be provided to be discussed at the combined report planning and database lock meeting (RPM/DBLM). At this meeting, all manual deviations identified at the sites by the Clinical Research Associate (CRAs) and deviations too complex to program will be reviewed by the trial team to decide which are considered important. For definition of iPDs, and for the process of identification of these, refer to the Boehringer Ingelheim (BI) Standard Operating Procedure (SOP) "Identify and Manage Important Protocol Deviations (iPD)" ([2](#)).

If any iPDs are identified, they are to be summarised into categories and will be captured in the RPM minutes (decision log) via an accompanying Excel spreadsheet ([3](#)).

The iPDs will be summarised and listed.

[Table 6.2: 1](#) below specifies which kind of iPDs could potentially lead to exclusion from which analysis set. The decision on exclusion of patients from analysis sets will be made at the latest at the Report Planning Meeting, after discussion of exceptional cases and implications for analyses.

Table 6.2: 1 Handling of iPDS

iPD code	iPD Category & Brief Description	Excluded from which analysis set
iPD A1	Inclusion Criteria Not Met	PKS, PDS, ECGPCS
iPD A2	Exclusion Criteria Met	PKS, PDS, ECGPCS
iPD B1	Informed consent not available/not done	All
iPD B2	Informed consent too late	None
iPD B3	Wrong informed consent form signed	All
iPD C1	Randomisation not followed	PKS, PDS, ECGPCS
iPD C2	Non-compliance	PKS, PDS, ECGPCS
iPD C3	Incorrect preparation (e.g. incorrect reconstitution of oral solution), administration or intake of trial medication	PKS, PDS, ECGPCS
iPD C4	Improper washout between treatments (Part II)	PKS, PDS, ECGPCS
iPD D1	Prohibited medication use	PKS, PDS, ECGPCS
iPD D2	Improper washout of prohibited concomitant medication	PKS, PDS, ECGPCS
iPD E1	Certain deviations from procedures used to measure primary or secondary data	PKS, PDS, ECGPCS
iPD F1	Certain deviations of time schedule used to measure primary or secondary data	PKS, PDS, ECGPCS
iPD G1	PDs affecting efficacy, safety and rights of subjects	PKS, PDS, ECGPCS
iPD Q1	Missed examination	PKS, PDS, ECGPCS
iPD Q2	Missed visit	PKS, PDS, ECGPCS
iPD Q3	Drug shipment	PKS, PDS, ECGPCS

6.3 SUBJECT SETS ANALYSED

Section 7.3 of the CTP: *For both trial parts, statistical analyses will be based on the following analysis sets:*

- *Treated set (TS): The treated set includes all subjects who were randomized and treated with at least one dose of study drug. The treatment assignment will be determined based on the first treatment the subjects received. The treated set will be used for safety analyses.*
- *Pharmacokinetic parameter analysis set (PKS): This set includes all subjects in the treated set (TS) who provide at least one PK endpoint that was not excluded due to a protocol deviation relevant to the evaluation of PK or due to PK non-evaluability (as specified in the following subsection 'Pharmacokinetics'). Thus, a subject will be included in the PKS, even if he [...] contributes only one PK parameter value for one period to the statistical assessment. Descriptive and model based analyses of PK parameters will be based on the PKS.*

[...]

Pharmacokinetics

[...]

Plasma and urine (in part I of the trial) concentration data and parameters of a subject will be included in the statistical pharmacokinetic (PK) analyses if they are not flagged for exclusion due to a protocol deviation relevant to the evaluation of PK (to be decided no later than in the Report Planning Meeting) or due to PK non-evaluability (as revealed during data analysis, based on the criteria specified below). Exclusion of a subject's data will be documented in the CTR.

Relevant protocol deviations may be:

- *Incorrect trial medication taken, i.e. the subject received at least one dose of trial medication the subject was not assigned to*
- *Incorrect dose of trial medication taken*
- *Use of restricted medications*

Plasma and urine (in part I) concentrations and/or parameters of a subject will be considered as non-evaluable, if for example:

[figure not shown]
- *The subject experienced emesis that occurred at or before two times median t_{max} of the respective treatment (Median t_{max} is to be determined excluding the subjects experiencing emesis),*

- *Missing samples/concentration data at important phases of PK disposition curve.*

In addition, plasma concentrations and/or parameters of a subject will be considered as nonevaluable in the BA part of the trial, if for example

- *The subject experiences emesis at any time during the labelled dosing interval.*
- *A predose concentration is >5% C_{max} value of that subject*

[...]

All ECG analyses in Part I are performed on the TS, except for the exposure-response analyses, which are performed on the ECGPCS defined below. The exposure-response analysis will only be performed if relevant findings for ECG parameters are found (the decision will be made during RPM).

- ECG Pharmacokinetic Concentration Set (ECGPCS):

This subject set includes all subjects of part I from the TS who provide at least one pair of a valid drug plasma concentration of BI 706321 and a corresponding (i.e. time-matched) ECG endpoint to be used in the exposure-response analyses. For placebo subjects, the plasma concentration is set to zero and hence always considered as valid. The decision whether a time deviation between PK blood sampling and ECG recording is acceptable (and thus whether the pair of values will be used) is to be made no later than at the RPM before data base lock.

Table 6.3: 1 Analysis sets for endpoints/data description

Endpoint/data description	TS	PKS	[REDACTED]	ECGPCS
Primary and further safety endpoints (incl. ECG)	X		[REDACTED]	
ECG endpoints and plasma concentrations used in exposure-response analysis (Part I only) – if needed				X
Primary/Secondary [REDACTED] endpoints			X	
Demographic/baseline data	X			
Important protocol deviations	X			
Disposition	X			

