Section 5.2.4.1 of the CTP: *Central ECG lab evaluation will be performed post-study per time point indicated in the CTP Flow Chart. For baseline, all 3 ECGs will be evaluated.*

This will include the determination of cardiac QRS-axis as assessed by the ECG machine's algorithm as well as the intervals RR, PR, QRS and QT measured semi-automatically. [...].

For the exposure response analyses, pairs of ECG variables and corresponding plasma concentrations will be built using the same planned time points, e.g. HR change from baseline and the plasma concentration measured at planned time 1:00 will build one pair. Whether a time deviation between PK blood sampling time and corresponding ECG

recording is too big and the pair has to be excluded from the analysis will be decided no later than at the RPM.

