7.8.4 ECG

Continuous safety ECG monitoring (by investigator)

Clinically relevant abnormal findings will be reported as adverse events.

No separate listing or analysis of continuous ECG monitoring will be prepared.

12-lead ECG – part I only

Abnormal findings will be reported as baseline conditions (at screening) or as AEs (during the trial) if judged clinically relevant by the investigator.

All evaluations of ECG data will be based on the TS, except the exposure-response analyses, which are based on the ECGPCS set.

Listing of individual data

For all quantitative endpoints, listings of individual data will be shown in Appendix 16.2. For QTcB and RR only listings will be provided. Occurrences of notable findings will be flagged.

Comments regarding the ECGs will be listed.

Categorical endpoints

For the categorical endpoints, frequency tables will be provided.

For all subjects with any notable finding in ECG intervals, a separate listing will be created as end-of-text display (based on the same display template as in Appendix 16.2), and the corresponding time profiles will be shown.

Quantitative endpoints

[figure not shown]
Descriptive statistics (N, mean, SD, min, median, max) will be provided for the changes from baseline over time of QTcF, QT, HR, PR and QRS. The time profiles of mean and SD for the changes from baseline on treatment will be displayed graphically by treatment.

For QTcF and HR changes from baseline, the relationship to the corresponding plasma concentrations will be evaluated using a random coefficient model. For subjects in the ECGPCS, all time points with available ECG endpoints and valid time-matched drug plasma concentrations will be included. For the handling of missing values, see [Section 6.6](#).

The response variable will be the change from baseline in QTcF (Δ QTcF). The placebo subjects will be included in the analysis ('Plc Total'), setting their plasma concentrations to zero.

[figure not shown]
As a first step, it is investigated if there is a potential delayed or accelerated (e.g. due to metabolites) effect of the drug on QTcF. A general visual impression is provided by overlaying time profiles of plasma concentrations and QTcF changes from baseline (Δ QTcF). These figures will be generated for each subject (presented in Statistical Appendix of the CTR), as well as for means per treatment group (presented in the End-of-Text part of the CTR).

[figure not shown]

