Appropriateness of heart rate correction methods of QT interval

[figure not shown]
To evaluate the appropriateness of the heart rate correction methods, the slope of the relationship of QTcF interval versus RR interval will be estimated separately for off-drug values and active treatment by applying the random coefficient model described in [Section 9.1.2](#) using the QTcF and RR variable values per time point. A scatterplot of QTcF vs RR including the overall regression line will be included in the Statistical Appendix of the CTR.

[figure not shown]

[figure not shown]

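### SAP 6.3 runs the Part I concentration-QTcF/HR model only if a results-based decision, taken with treatment known, calls for it; the model should be run in all cases

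*SAP*

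**What the plan says.** SAP 6.3 defines the ECG Pharmacokinetic Concentration Set (ECGPCS) and limits its use: "The exposure-response analysis will only be performed if relevant findings for ECG parameters are found". It leaves the decision to the Report Planning Meeting (RPM). Table 6.3:1 carries the same limit: "ECG endpoints and plasma concentrations used in exposure-response analysis (Part I only) – if needed".

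The analysis itself is already specified. SAP 6.7 sets the pairing: "For the exposure response analyses, pairs of ECG variables and corresponding plasma concentrations will be built using the same planned time points". SAP 7.8.4 names the method: "For QTcF and HR changes from baseline, the relationship to the corresponding plasma concentrations will be evaluated using a random coefficient model". Placebo subjects from all dose groups enter the model with concentration zero. A delay check comes before the model: "As a first step, it is investigated if there is a potential delayed or accelerated" effect on QTcF.

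The rest of 7.8.4 carries no such condition. It covers listings, frequency tables, mean and SD profiles, and summaries: "Descriptive statistics (N, mean, SD, min, median, max) will be provided for the changes from baseline over time". It also includes a check of heart-rate correction, in which "the slope of the relationship of QTcF interval versus RR interval will be estimated separately for off-drug values and active treatment".

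SAP 6.2 combines the RPM with the database lock meeting. Protocol 4.1.5.1 has all Part I data handled open label, lists the statistician, trial leader, pharmacokineticist and pharmacometrician as unblinded, and blinds the central ECG staff who measure the intervals. Protocol 7.3.4 leaves the ECG endpoints and their analyses to the SAP.

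**The concern.** Whether the model is run depends on what the ECG data show, as judged by people who know treatment. Both outcomes have a cost.

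- **A finding is declared.** The slope is then reported only because something was seen, so it is open to selection.
- **No finding is declared.** The model is dropped. Yet this is when an upper bound on the drug effect is most useful, because a table with nothing striking in it does not say how large an effect remains compatible with the data.

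The question is one the protocol itself raises. Section 1.3.2.3 reports QT/QTc prolongation in monkeys at exposures about 12 times the trial's exposure cap, and section 1.4.3 rates the human risk as low. A slope with an interval would put a number on that for later trials. The stake is estimation only: QTc is not a primary endpoint and Part I tests no hypothesis.

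**Working it through.** The plan states no power, precision or sample-size figure for the ECG analysis, so there is none to reproduce. The check sets the sections side by side and counts the data.

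**1. Nature of the condition.** SAP 6.3 ties the analysis to ECG findings, and the RPM decides. The central ECG evaluation is post-study (protocol 5.2.4.1) and data handling is open label (protocol 4.1.5.1). The decision is therefore results-based and taken with treatment known. This holds whatever section 9 says about thresholds.

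**2. What is left without the model.** In the visible text: N, mean, SD, minimum, median and maximum of change from baseline by time point, frequency tables, listings and profiles. The QTcF-versus-RR slope stays, but it assesses the heart-rate correction and does not estimate a drug effect.

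**3. Data available to the model.** Inputs: eight dose groups of 8, with 6 active and 2 placebo (SAP 6.1). Centrally read post-dose ECGs number 10 in the four groups below 4 mg and 12 in the four groups from 4 mg upward (SAP Table 6.7:1). The flow charts show a PK sample at each of these times.

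- All pairs: 32 × 10 + 32 × 12 = 320 + 384 = 704
- Active: 24 × 10 + 24 × 12 = 240 + 288 = 528
- Placebo: 8 × 10 + 8 × 12 = 80 + 96 = 176

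These are planned counts for each endpoint, with full enrolment and nothing missing.

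**4. Why the summary tables are not a full substitute.** They take one dose group (6 active) and one time point at a time. SAP section 7 also splits placebo by formulation in the safety evaluation: 3 solution groups × 2 = 6, and 5 capsule groups × 2 = 10. The model uses all doses, all paired times and all 16 placebo subjects. A reader could form an interval from the tabulated N, mean and SD, although the SAP plans none. In units of the SD at that time point, the 90% half-widths would be:

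- One dose group alone: t(0.95; 5)/√6 = 2.015/2.449 = 0.82 SD
- A capsule dose group against capsule placebo, with a common SD and at times up to 24 h: t(0.95; 14) × √(1/6 + 1/10) = 1.761 × 0.516 = 0.91 SD

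Preliminary median tmax for 0.3 to 8 mg was 4.5 to 6 h (protocol Table 1.2.3:1). That falls between the 4 h and 8 h ECGs, so the tables for those groups have no reading at the typical peak.

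**5. What cannot be computed.** The visible text gives no threshold for the condition, so no size can be put on the selection effect. The documents give no SD for change in QTcF, so no half-width in ms can be derived for the model or the tables.

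**The case against.** The strongest case against has four parts.

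**Text is missing.** SAP section 9 is not in the supplied document, although visible text cites 9.1.2 for the random coefficient model and 9.1.3 for new-onset QTc categories. Section 7.8.4 is also cut: a first step is announced and no second step is visible. A reader might infer that the trigger is undefined, or that no interval is planned anywhere. The documents do not support either claim, because the definition or the interval may stand in the unseen text. This part of the objection stands. It does not remove the condition, which 6.3 states outright.

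**The sections fit together.** A reader might infer that 7.8.4, which states the model without the condition, contradicts 6.3. It does not. Section 7.8.4 bases the exposure-response analyses on the ECGPCS, which is defined in 6.3 next to the condition. One section says whether and the other says how.

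**The analysis is exploratory.** Protocol 7.2 plans no hypothesis test in Part I, section 5.3.4 makes PK-PD work optional, and section 7.3.4 calls the safety analyses descriptive. The interval readers are blinded, which protects the measurements. All of this stands and limits the weight of the point. But protocol 7.2 treats any confidence interval as an interval estimate, so reporting one fits the protocol.

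**No timing inference.** A reader might infer that the condition was written with the answer known, because protocol 1.2.3 (July 2020) reports no relevant ECG changes and the SAP is dated January 2021. That statement rests on clinical monitoring, and the central evaluation is a separate post-study step. The documents do not show that central results were known.

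**Conclusion.** The point holds as a cheap improvement to an exploratory safety analysis. An already specified model is made to depend on a results-based decision taken with treatment known. If that decision is negative, the visible plan gives no model-based estimate or bound for the drug effect on QTcF or heart rate, although about 704 planned pairs per endpoint (528 active, 176 placebo) would allow one. The ECGs would still be listed and summarised; what goes unused is their pairing with concentration.

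The point is not an error in a stated figure, and no harm is shown. A reader might want a loss of precision in ms, but that would need a QTcF variance, an exposure variance and a random-slope variance that the documents do not give, so none is claimed. The conclusion rests on the visible text of SAP 6.3 and 7.8.4 and on the planned group sizes.

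**What to change.** In SAP 6.3, delete the sentence that makes the exposure-response analysis conditional; in Table 6.3:1, delete 'if needed'. In 7.8.4, state that:

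- the QTcF and HR model is run in all cases, as specified there and in section 9, after the delayed-effect check;
- the result is labelled exploratory;
- the slope and the predicted change from baseline at the final geometric mean Cmax of the highest dose group are reported, each with a two-sided 90% CI unless section 9 already sets the interval;
- any suspected delay is stated beside the estimate as a limit on its interpretation.

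The final Cmax is needed because protocol 7.4 keeps preliminary PK results out of the trial report.

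The cost is a little extra programming and reporting for two endpoints, with no new data, visits or samples. The downside is an estimate that is harder to interpret if a delay is seen.

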6.5 POOLING OF CENTRES

This section is not applicable, because the study was performed in only one centre.

6.6 HANDLING OF MISSING DATA AND OUTLIERS

Handling of missing data and outliers will be performed as described in the CTP, [Section 7.5](#).

The only exceptions where imputation might be necessary for safety evaluation are AE dates. Missing or incomplete AE dates are imputed according to BI standards (see 001-MCG-156_RD-01 ([4](#))).

Missing data and outliers of PK/[REDACTED] are handled according to BI standards (see 001-MCS-30-476) ([5](#)).

If single cardiac cycles of an ECG (out of the generally four) are missing, the arithmetic mean for this single ECG will be computed with the reduced (1, 2 or 3) number of cardiac cycles.

If replicate ECG recordings are missing, the arithmetic means per time point will be computed with the reduced number (1 or 2) of recordings.

For the classification of the on-treatment QTc/QT intervals into ‘no new onset’ / ‘new onset’ categories, the handling of missing value is described in Appendix [Section 9.1.3](#).

For placebo subjects the missing plasma concentration values will be replaced by 0 for the exposure response analysis. For subjects on active drug, missing plasma concentration values with 'BLQ' in the comment field will be replaced by $\frac{1}{2}$ LLOQ.

6.7 BASELINE, TIME WINDOWS AND CALCULATED VISITS

The baseline value is defined as the last measurement before first administration of BI 706321 or Placebo in each treatment period.

The baseline for analysis of laboratory data is the last measurement before first administration of study drug (e.g. ptm -1:30 (part I), screening (part II)).

Section 6.1 of the CTP: *Exact times of measurements outside the permitted time windows will be documented. The acceptable time windows for screening and the end of trial examination are provided in the CTP Flow Chart.*

Study measurements and assessments scheduled to occur 'before' trial medication administration on Day 1 are to be performed and completed within a 3 h-period prior to the trial drug administration (including blank values for PK and biomarkers).

The acceptable deviation from the scheduled time for vital signs, ECG, and laboratory tests will be ± 15 min for the first 4 h after trial drug administration, ± 30 min thereafter on Day 1, ± 60 min on Day 2, and ± 120 min from 48 h post administration onwards.

[...] Starting from 48 h post administration a deviation from the scheduled time for PK [REDACTED] sampling of ± 120 min is acceptable.

Adherence to time windows will be checked via the consistency check listings at the RPM/DBLM.

There will be a centralised evaluation of the 12-lead ECG recordings at the time points and for the ECG recordings specified in the [Table 6.7: 1](#) below:

Table 6.7: 1 Time schedule of 12-lead ECG recordings – Part I

Visit	Day	Planned time [hh:mm] (relative to drug administration)	Study phase	Central evaluation
1	-21 to -1		Screening	NA
2	1	-02:00	Baseline	All 3 single ECGs
		-01:45		
		-01:30		
		00:30		Single ECG
		01:00		Single ECG
		01:30		Single ECG
		02:00		Single ECG
		02:30		Single ECG
		03:00		Single ECG
		04:00		Single ECG
		08:00		Single ECG
		12:00		Single ECG
	2	24:00		Single ECG
		34:00		NA (dose groups 1, 2, 9, 11) Single ECG (dose groups 3-8)
	3	48:00		NA (dose groups 1, 2, 9, 11) Single ECG (dose groups 3-8)
3	15 to 22		End of trial examination	NA

At Visits 1 and the End of trial examination single ECGs will be recorded, as well as at visit 2. At visit 2 ECGs will be centrally evaluated.

All single ECGs will be transferred to the database. The baseline value of an ECG variable is defined as the mean of the transferred baseline ECG measurements prior to drug administration.

Section 5.2.4.1 of the CTP: *Central ECG lab evaluation will be performed post-study per time point indicated in the CTP Flow Chart. For baseline, all 3 ECGs will be evaluated.*

This will include the determination of cardiac QRS-axis as assessed by the ECG machine's algorithm as well as the intervals RR, PR, QRS and QT measured semi-automatically. [...].

For the exposure response analyses, pairs of ECG variables and corresponding plasma concentrations will be built using the same planned time points, e.g. HR change from baseline and the plasma concentration measured at planned time 1:00 will build one pair. Whether a time deviation between PK blood sampling time and corresponding ECG

recording is too big and the pair has to be excluded from the analysis will be decided no later than at the RPM.

7. PLANNED ANALYSIS

The placebo group in the safety evaluation will consist of all placebo treated subjects, regardless of the dose group in which they were treated but separated by pharmaceutical formulation (capsule and oral solution).

Trial Parts will be reported separately if not otherwise stated.

Safety analysis (refer to [Section 7.8](#)) will be performed by [REDACTED] and will be presented in Sections 15.1 to 15.4 of the CTR and in Appendix 16.2 and 16.1.13.1.

Inferential statistical analyses of PK endpoints (refer to Section [7.5.2](#)) will also be performed by [REDACTED] and will be presented in Section 15.5 of the CTR and in Appendix 16.1.13.3.

Descriptive data analysis of PK [REDACTED] parameters and concentrations will be performed by the department [REDACTED] at [REDACTED] and will be presented in Sections 15.6 and 15.7 of the CTR and in Appendices 16.1.13.5 and 16.1.13.6.

The format of the listings and tables will follow the standards defined in the BI corporate guideline “Reporting of Clinical Trials and Project Summaries” [001-MCG-159] ([6](#)) with the exception of those generated for PK-calculations.

The individual values of all subjects will be listed, sorted by treatment group (Part I) / treatment sequence (Part II), subject number, and visit and actual treatment (Part II). The listings will be included in Appendix 16.2 of the CTR.

For end-of-text tables, the set of summary statistics for non-PK parameters is:

N	number non-missing observations
Mean	arithmetic mean
SD	standard deviation
Min	minimum
Median	median
Max	maximum

For analyte concentrations, the following descriptive statistics will additionally be calculated:

CV	arithmetic coefficient of variation
gMean	geometric mean
gCV	geometric coefficient of variation

For PK parameters, the following descriptive statistics will additionally be calculated:

CV	arithmetic coefficient of variation
gMean	geometric mean
gCV	geometric coefficient of variation

P10	10th percentile
Q1	1st quartile
Q3	3rd quartile
P90	90th percentile

The data format for descriptive statistics of concentrations will be identical with the data format of the respective concentrations. The descriptive statistics of PK parameters will be calculated using the individual values with the number of decimal places as provided by the evaluation program. Then the individual values as well as the descriptive statistics will be reported with three significant digits in the CTR.

Tabulations of frequencies for categorical data will include all possible categories and will display the number of observations in a category, as well as the percentage (%) for each treatment group. Percentages will be rounded to one decimal place and will be based on all subjects in the respective subject set whether they have non-missing values or not. The category 'missing' will be displayed only if there are actually missing values.

Units of variables should be given in the titles or column/row descriptors in square brackets (e.g. [mg]).

Exclusion of PK parameters

The ADS ADPP (PK parameters) contains column variables APEXC and APEXCO indicating inclusion/exclusion (APEXC) of a PK parameter and an analysis flag comment (APEXCO). All analyses based on the PKS will include parameters if they are not flagged for exclusion, that is APEXC is equal to "Included".

Exclusion of PK concentrations

The ADS ADPC (PK concentrations per time-point or per time-interval) contains column variables ACEXC or ACEXCO indicating inclusion/exclusion (ACEXC) of a concentration and an analysis flag comment (ACEXCO). Exclusion of a concentration depends on the analysis flag comment ACEXCO. For example, if ACEXCO is set to 'ALL CALC', the value will be excluded for all types of analyses based on concentrations. If ACEXCO is set to 'DESC STATS', the value will be excluded from descriptive evaluations per planned time point/time interval. If ACEXCO contains the addition 'TIME VIOLATION' or 'TIME DEVIATION', the value can be used for further analyses based on actual times. If ACEXCO is set to 'HALF LIFE', the value will be excluded from half-life calculation (and, as a consequence, any calculation that relies on λ_z) only; the value is included for all other analyses.

Further details are given in 001-MCS-30-476 "TMCP Data Analysis" ([5](#)).

